Therefore, we are developing methods for using a person's own behavior in daily life as a replacement for controlled laboratory research protocols. We will apply these new methods to evaluate the differences in behavior among specific biomechanical devices such as prostheses, orthoses, or types of footwear. The potential benefits of this approach include eliminating the need for laboratory protocols in some instances, and improving the ecological validity of data used to determine the benefits of different treatments, due to recording during unsupervised real-world movements.

The scientific approach is to evaluate the statistical differences among aggregated samples of movements on frequently repeated paths in everyday life, under different experimental conditions (such as different prostheses, orthoses or shoes). We will track a person's movements outside and inside buildings using wearable inertial sensors, environmental sensors (e.g., barometric pressure, temperature, humidity), and location sensors (e.g., GPS, computer network signals, dedicated beacons). We will identify specific paths (sidewalks, hallways, stairways, corners, etc.) that are frequented by an individual. We will identify each bout of movement along these paths and build sets of “comparable bouts” on the same path across multiple days and experimental conditions. We will repeat this procedure for multiple different devices and compare the effects of these devices on habitual movement.

Project Goals:

The immediate goals of this project are (i) to compare the effects of different types of features

in lower limb prostheses and orthotic solutions; and (ii) to develop methods for analyzing the effects of mobility devices on locomotion in real-world environments.

Aims

Aim 1:

To develop methods for using wearable sensors and long-term monitoring to assess changes in gait due to different mobility interventions, and to study the effects of different interventions using these techniques.

Aim 2:

To compare the effects of different features of prosthetic feet on movement quality in everyday life.

Aim 3:

To compare the effects of different orthotic treatments on movement quality in everyday life.

Study Objectives

Primary objective

To determine the comparative biomechanical benefits of prosthetic foot-ankle systems with different features to persons with lower-limb amputation.

Secondary objectives

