To determine the comparative biomechanical benefits of different orthotic solutions to persons with drop-foot.

Tertiary objective

To perfect methods for collecting and analyzing data from wearable sensors to compare the benefits of different conditions on everyday movement.

Study Outcomes

Primary outcome

The primary outcome is biomechanical gait function, as measured through gait metrics such as limb and joint movement patterns and foot placement variability (kinematics), and joint and prosthetic socket loads and joint power production (kinetics).

Secondary outcome

The secondary outcome is behavioral gait function, as measured from preferred walking speed, stride count, breadth and perceived ease of locomotor activities, and reports of inconvenience, pain and discomfort.

Research Design and Methods

In this protocol we will perform short-term laboratory and long-term real-world locomotion testing with a variety of commercially available lower limb prostheses and commercially available orthotic solutions for drop-foot, with emphasis on using wearable sensors to compare biomechanical performance with different devices.

Subjects will perform testing inside the laboratory (“lab testing”), outside the laboratory (“field testing”) on and near the campus of UW-Madison, and/or extended testing in a home and community environment (“take-home testing”) to evaluate different aspects of device function. Lab testing may consist of standing (on one or both legs), walking (at various speeds, forward and backward), and running (from running in place to a fast jog) trials, performed on a standard treadmill, an instrumented split-belt treadmill, a moving treadmill with virtual-reality surround screen, on ramps, on stairs, and/or on the floor. Measurements will be made using standard biomechanical measurement tools such as motion capture, wearable motion sensors, force transducers, pressure insoles, electromyographic electrodes, treadmills, and respiratory gas sampling equipment. Field testing may include standing and walking trials, conducted indoors and outdoors, on level ground, uneven ground, slopes, and stairs, as well as level running. Take-home testing will consist of wearing one or more different prostheses, orthoses, or types of footwear, together with wearable sensors to evaluate their function, for periods ranging from hours to weeks of everyday life.

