- Subjects involved in running tests must be able to run for 30 minutes (total) in bouts of at least 6 minutes, without becoming fatigued, feeling dizzy, having chest pain, or experiencing claudication symptoms.
- Subjects must have no known cognitive disability.
- Subjects must be fluent in spoken and written English.
- Running portions of the study will be limited to subjects who self-report regular engagement in recreational or competitive running.
- Subjects in the branch that uses only their own prostheses must have at least a daily use prosthesis and a running-specific prosthesis; additional prostheses may also be included.

Control Subjects:

- Ages 18-75 years
- Subjects should consider themselves in good health, and be able to perform typical activities of daily living (ADL).
- Subjects may use a narrow-base cane (single point, narrow tripod base, etc.) as an ambulatory aid but not a small-base quad cane, wide-base quad cane or walker.
- Subjects must be able to walk for 30 minutes (total) and stand for 30 minutes (total), in

individual bouts of at least 6 minutes, without becoming fatigued, feeling dizzy, having chest pain or shortness of breath, or experiencing claudication symptoms.

- Subjects involved in running tests must be able to run for 30 minutes (total) in bouts of at least 6 minutes, without becoming fatigued, feeling dizzy, having chest pain, or experiencing claudication symptoms.
- Subjects must have no known cognitive disability.
- Subjects must be fluent in spoken and written English.

Multiple Sclerosis group:

- For the specific subgroup targeting Multiple Sclerosis, subjects must have a clinical diagnosis of Multiple Sclerosis and a clinician must determine they are experiencing foot drop.
- Subjects must be able to comfortably wear and ambulate with both study devices with effective management of foot-drop, without significant discomfort

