Justification of Altered Consent: This study involves completing a telephone screening, questionnaires, and participating in clinical assessments and interventions that are common and currently in use in clinical practice at UW Health. These activities are similar to and of no greater risk than activities of daily living or that would be encountered during a standard clinic examination. The altered consent increases the feasibility of conducting this project (and future projects) by simplifying recruitment. These procedures also reduce the time commitment required of participants. This waiver would not adversely affect the rights and welfare of subjects.

Written Informed Consent: A copy of the informed consent document will be provided to potential participants after screening via e-mail or U.S. mail according to participants preference. Subjects will be asked to return a signed copy of written consent either via a scanned copy emailed to the study team or a signed copy sent to the study team through U.S. mail. Alternatively, subjects can provide Written Informed Consent through REDCap.

The informed consent will be cosigned prior to the start of the first data collection visit at the BADGER Laboratory. Each consented participant will be reminded that s/he may withdraw from the study at any time, for any reason, without any impact on his/her ongoing care.

Subject Compensation:

- On-site testing studies (in-lab or out-of-lab) with no take-home component:
 - Subjects in the Patient groups (users of prostheses or orthoses) will be paid \$20 per hour to compensate for their time and travel expenses.
 - Subjects in the Non-patient group will be paid \$10 per hour for laboratory sessions to compensate for time and travel expenses.
 - Subjects will be reimbursed for parking expenses (or a parking voucher will be provided).
- Long-term monitoring studies (take-home studies):
 - Subjects in the Patient groups (users of prostheses or orthoses) will be paid up to \$450 total for participation, including on-site portions:
 - Up to \$360 will be paid on a pro-rata basis based on how much of the study the subjects complete (at \$40 per week for Orthosis users, \$90 per week for Prosthesis users).
 - \$90 will be paid for completion of the full study.
 - Subjects in the Non-patient group will be paid up to \$150 total for participation, including on-site portions:

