Specific Procedures – Comparing Prostheses and Orthoses using Real-World Data

Study Design:

Subjects will wear one or more movement sensors on various body segments, especially the foot, as well as means of logging location data (e.g. a GPS, Bluetooth, Wifi receiver and/or cell phone app). Subjects will wear (movement sensors) and/or carry (phone) these sensors during extended measurement periods of up to three weeks per experimental condition, for up to four conditions (prostheses, orthoses or footwear). We will combine movement and location data to identify the most-frequently-repeated paths a person takes, and finally analyze movement along these paths to identify changes in mobility performance (**Figure 6**). We will also perform standard biomechanical analyses of posture and movement in the laboratory.

NOTE: Because part of this study is the development of these methods, we may change the number of sensors, which sensors are used, how they are worn/carried, how long the take-home tests are, the devices under study, and other details of the study, within the limits approved in the *Study Procedures – General* section of this protocol.

[figure not shown]

Figure 6: Example self-test by the experimenters showing highly repeated straight walking trajectories found from a 10-day walking test. The experimenter wore athletic shoes and sandals for 5 days each, indicated by solid lines and dashed lines respectively. The same color indicates same paths. Blue and red lines are walking trajectories in the hallway between the subject's office and the restroom and water fountain (different directions are separated into two different paths). Yellow lines represent the sidewalk between the building where the subject works and a nearby bus stop. Purple lines represent a sidewalk between the same building and a dining location.

Test Conditions:

- Prosthetics branch 1: Participants with amputation will use 2-4 prosthetic feet from different categories, each fit to their standard socket by a professional prosthetist.
 - Participants will use each prosthesis for a take-home test of 1-3 weeks of everyday life. Comparisons will include energy-storage-and-return prostheses (ESR) vs. prostheses with a passive hydraulic ankle (PHA) vs. prostheses with a microprocessor ankle (MPA) (**Figure 1**). Comparisons may also include Articulated ESR (AESR) prostheses, which have one or more additional joints in the mechanism, or other types of standard commercial prostheses.

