- Most likely measurements include: miniature inertial sensors, GPS, Bluetooth and Wifi location from a wearable receiver or cell phone app, force plate/force treadmill, EMG, motion capture, indirect calorimetry, and voice/photo/video recording.

Intended Outcome - Primary:

The primary outcome is the measured difference in stride length at identical walking speed when using different prostheses, orthoses, or footwear. We expect to observe increased stride length when using more compliant prostheses or the FES neuro-orthosis.

Intended Outcomes - Secondary:

The secondary outcomes include other measures of gait performance determined from the same system. Stride width, stride clearance, speed, stride frequency, ground reaction forces, and measures of gait regularity are among many analyses that will be performed with the data from this experiment.

Data and Safety Monitoring Plan

The PI will oversee compliance with the data and safety monitoring plan to ensure adherence to IRB guidelines. All researchers and research staff involved in the study are required to maintain Human Subjects and HIPAA training and will be continuously involved in data and safety monitoring. Data and safety monitoring will occur on a continuous basis.

Adverse events or problems will be reviewed by the principal investigator as they occur and reported to the IRB in accordance with posted guidelines at the “Events Requiring Reporting to the IRB” page: <https://kb.wisc.edu/hsirbs/18324>.

Data Processing/Data Analysis:

Electromyographic, kinematic, kinetic, and metabolic data will be compared with different lower limb prostheses, orthoses and footwear, using repeated measures ANOVAs. In initial experiments measuring movement performance with only the subject’s own devices, we will use repeated measures ANOVAs to compare performance variables (e.g. EMG amplitude, gait economy, joint range of motion, peak ground reaction force) under different conditions (e.g. locomotion speed, incline, motor task). Corrections for multiple comparisons will be made using False Discovery Rate adjustments [51], [52]. In analysis of experimental conditions, we will use the new methods developed in this research for analyzing the same types of movement information, isolated to frequently-repeated paths in everyday life. We may also analyze specific events of interest such as slips, trips or falls that occur in everyday life and are recorded by the wearable sensors [53].

Sample size

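### Branch 1 allows two to four feet but compares at least three, so a mixed model that keeps participants with incomplete device sets is a cheap improvement on the named repeated measures ANOVA

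*Combined protocol and SAP*

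**What the plan says.** All references are to the combined protocol and SAP.

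- **Data Processing/Data Analysis:** "Electromyographic, kinematic, kinetic, and metabolic data will be compared with different lower limb prostheses, orthoses and footwear, using repeated measures ANOVAs". A second sentence uses the same method for the subject's own devices under different speeds, inclines and tasks. False Discovery Rate adjustment is planned. Everyday-path data are left to methods still being developed in the project.
- **Test Conditions, prosthetics branch 1:** "Participants with amputation will use 2-4 prosthetic feet from different categories". The same item continues: "Comparisons will include energy-storage-and-return prostheses (ESR) vs. prostheses with a passive hydraulic ankle (PHA) vs. prostheses with a microprocessor ankle (MPA". Further foot types may be added.
- **Inclusion criteria, own-prosthesis branch:** "Subjects in the branch that uses only their own prostheses must have at least a daily use prosthesis and a running-specific prosthesis".
- **Subject Compensation:** part of the payment "will be paid on a pro-rata basis based on how much of the study the subjects complete", and a further $90 is paid for completing the full study.
- **Sample size:** 10 participants per test. **Target Population and Enrollment:** 20 persons with transtibial amputation.
- **Intended Outcome - Primary** (real-world section): "The primary outcome is the measured difference in stride length at identical walking speed when using different prostheses, orthoses, or footwear".

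No section gives a rule for participants who lack one of the compared devices.

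**The concern.** A participant who uses two feet cannot supply all of ESR, PHA and MPA. This follows from the design and needs no dropout. In its classical three-level form, repeated measures ANOVA needs every level from every participant, so a two-foot participant adds nothing to the three-way test, although the pair of feet actually used is informative. With 10 people per test, each such person matters.

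The issue is confined to comparisons of three or more devices. The orthotics branch compares two devices. In the own-prosthesis branch the daily-use and running-specific pair is complete by eligibility. In both, a level goes missing only through dropout, and a participant with one of two devices carries almost no within-person information under any model.

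A smaller matter lies beside it. The real-world primary outcome is defined at identical walking speed, but no step says how that is reached. The only matching described, in Real-World Movement Assessment, groups bouts "on the same path across multiple days and experimental conditions", and sharing a path does not by itself equalise speed.

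**Working it through.** **1. The plan's own figures.** The formula in the Sample size section is N = 2 × ((1.96 + 0.84) × SD/d)².

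- Push-off work, 3.1 ± 1.5 J: 2 × (2.80 × 1.5/3.1)² = 3.67, rounded up to 4.
- Collision work, 0.055 ± 0.04 J/kg: 2 × (2.80 × 0.04/0.055)² = 8.29, rounded up to 9.

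Both match the stated 4 and 9. The planned 10 takes it that all 10 contribute to a comparison.

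**2. Participants per pairwise contrast.** Let n3 participants use all three feet and n2 = 10 − n3 use two, spread evenly over the three pairs. The three-level ANOVA keeps n3. Separate pairwise tests keep n3 + n2/3 per pair. A within-participant analysis of everyone has effective n = n3 + n2/2.

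- n2 = 3: 7, 8 and 8.5.
- n2 = 6: 4, 6 and 7.

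**3. Power of the three-foot F test.** From the documents: n = 10 and alpha 0.05. Assumed: effects 0/0.5/1.0, within-person SD s = 0.7, and which foot is missing is unrelated to outcome. Sums of squares of the effects within a participant:

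- Three feet: 0.25 + 0 + 0.25 = 0.5.
- Two feet: 0.125, 0.125 or 0.5 depending on the pair, mean 0.25.

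For complete sets, the noncentrality is 0.5 × n3/s² with 2 and 2(n3 − 1) df. With everyone kept it is (0.5 × n3 + 0.25 × n2)/s², with 2 and (3 × n3 + 2 × n2 − 12) df, where 12 is 10 participants plus 2 device contrasts.

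| Incomplete | Complete sets: noncentrality, df | Power | All kept: noncentrality, df | Power |
|---|---|---|---|---|
| 0 | 10.20, 18 | 75% | 10.20, 18 | 75% |
| 1 | 9.18, 16 | 69% | 9.69, 17 | 72% |
| 3 | 7.14, 12 | 55% | 8.67, 15 | 66% |
| 5 | 5.10, 8 | 37% | 7.65, 13 | 59% |

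A mixed model also uses some between-person information. In simulation it gave 74, 67 and 59% in the last three rows.

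**4. Dependence on effect size.** The plan's two ratios can be used if their SD is read as that of a within-person difference (an assumption; neither concerns stride length). Then s = (SD/d)/√2 when the largest difference is set to 1.

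- 0.055/0.04 (s = 0.514): 82 vs 91% with 3 incomplete.
- 3.1/1.5 (s = 0.342): 99 vs 100% with 3 incomplete.
- Weaker effects, s = 0.9: 36 vs 44% with 3 incomplete.

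**5. Unequal device variances.** A random-intercept model assumes equal variances and, with complete sets, essentially reproduces the uncorrected ANOVA. Under the null with 10 complete sets (100,000 simulated data sets), the uncorrected F test rejects 6.9% at device SDs 0.35/0.7/1.4 and 7.9% at 0.3/0.3/1.2. A Greenhouse-Geisser correction gives 5.0% and 5.2%. The model therefore needs a sensitivity check.

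**6. Speed.** If speed were not equalised, the spurious stride-length difference would be slope × speed difference. With assumed slopes of 0.4 to 0.8 m per m/s and differences of 0.03 to 0.10 m/s, it runs from 0.4 × 0.03 = 1.2 cm to 0.8 × 0.10 = 8 cm. This is what the unstated step has to remove. A rigid rule that each path must show overlapping speeds is fragile: with assumed within-path speed SD 0.08 m/s and a 0.10 m/s difference, about 0.1% of two-device paths lack overlap with 15 bouts per device, 13% with 5 and 35% with 3.

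**The case against.** A reader might infer that the plan discards two-foot participants. It does not say so. The section speaks of ANOVAs in the plural, which leaves pairwise tests open, and step 2 shows those lose less. An ANOVA with participant as a block would recover most of the gain too.

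The documents may also avoid the problem altogether. The 20 transtibial participants exceed the 10 per test, so 10 complete three-foot sets may be available; the split is not given. The two-to-four range may vary between tests and not between people within one test. Prosthesis users can earn $360 at $90 per week, that is four weeks, and the section on the relationship between the sites describes one-week periods at UW-Madison. One possible reading is up to four conditions per person, enough for all three categories, although Test Conditions allows one to three weeks each. Pro-rata payment is weak evidence of incomplete sets, since completion is also rewarded. These points stand. They make the number incomplete unknown, and it could be zero. They do not supply a rule for the case where it is not zero.

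A reader might also infer that the primary outcome is biased by walking speed. The documents do not support that. The outcome is defined at equal speed, so the bias in step 6 arises only if that definition is ignored. How to analyse repeated paths is an aim of the project, and the Study Design note lets details change within approved limits. What remains is a step not yet written down.

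**Conclusion.** The point holds as a cheap improvement for branch 1 comparisons of three or more feet. At n = 10 under the step 3 assumptions, keeping everyone adds 0, 3, 11 and 22 percentage points of power with 0, 1, 3 and 5 incomplete sets. The comparator is a three-level complete-set ANOVA; against pairwise ANOVAs the gain is smaller. It is nil with complete sets, small when effects are large, and essentially nil in two-device tests.

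The effects, the SD and the number incomplete are all assumed; the documents give none of them for stride length. The figures therefore illustrate a range and do not estimate a loss in this trial. The walking-speed matter is a secondary clarification and not an error in the plan.

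**What to change.** For device comparisons, replace the quoted ANOVA sentence with wording such as: *One value per participant and device (per test condition in the laboratory) is analysed in a linear mixed model with device as a fixed effect, participant as a random effect and Kenward-Roger or Satterthwaite degrees of freedom, including every participant with at least two of the compared devices.* Add a sensitivity check for unequal device variances, for example a Greenhouse-Geisser ANOVA on complete sets, or paired contrasts. Keep the False Discovery Rate adjustment and the second ANOVA sentence on speed, incline and task.

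As a clarification, state before patient data are compared by device how stride length is brought to equal speed. One option is regression on speed within participant, evaluated at a common speed. Report how many participants and paths lack speed overlap, but do not make path-by-path exclusion mandatory, because it would tend to lose the participants whose speed changes most.

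The cost is SAP wording and a little more analysis. Variance components will be imprecise at about 10 people, and the model gives no protection if a foot is missing for reasons related to outcome, so those reasons should be reported.

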For specific tests with a goal of publication, the sample size will be 10 participants. Studies with between 6 and 12 participants are common in the field, and have proven sufficient to

demonstrate many effects in a variety of studies of gait mechanics in persons using prostheses and orthoses [19], [54]–[61]. We estimate sample size from data on changes in gait mechanics across conditions with a past novel prosthesis [54], [56].

The sample size required per group is computed using the following formula:

$$N \text{ (per group)} = 2 * ((z(1-\alpha/2) + z(\beta)) * \sigma / d)^2,$$

where d is the expected difference in outcome value, post- vs. pre-training; σ is the estimated standard deviation; α is the alpha error we would like to control; and β is the statistical power. Here we set a statistical goal of 80% power ($\beta = 0.80$, $z(\beta) = 0.84$) and α level 0.05 ($z(1-\alpha/2) = 1.96$).

Based on changes gait mechanics with a past novel prosthesis, we expect: a difference in ankle push-off of 3.1 ± 1.5 J across several conditions [54], or a difference in opposite-leg collision work of 0.055 ± 0.04 J/kg [56]. These give sample size estimates of 4, and 9 subjects, respectively. This sample-size estimate is conservative, as it uses a two-tailed test when in fact we expect to test for specific changes (one-tailed test), and it does not account for repeated-measures structure in our experimental design. Therefore we expect 6-10 subjects to provide sufficient statistical power. We plan to use 10 subjects for the tests of prostheses and orthoses at UW Madison.

Analysis of Remotely-Collected Data

Data from UW-Madison studies, and separately from WRNMMC studies, will be analyzed at both sites, but primarily UW-Madison. Data from in-lab biomechanics studies as well as take-home studies with wearable sensors will be transmitted between sites. Personnel at both sites may be involved in analyzing the biomechanical data (movement patterns, joint loads, etc.) and interpreting the location-based data (e.g. speed, stride length, limb load) recorded from everyday life. Data transmission will use HIPAA-compliant Box folders, HIPAA-compliant folders on UW's Campus Computing Initiative (CCI) systems, or other HIPAA-compliant means approved by the DOD. Only coded data will be transmitted; each site will retain the only copy of its respective code key linking subject numbers to their direct identifiers, and the other site will not receive this information.

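### Does the claim that 6 to 10 participants give enough power, with no calculation for stride length, call for a change to the sample size section?

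*Combined protocol and SAP*

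**What the plan says.** The Sample size section uses a formula for two independent groups, with two-sided alpha 0.05 and 80% power. Its inputs are a push-off difference of 3.1 ± 1.5 J and a collision-work difference of 0.055 ± 0.04 J/kg, both from studies of an earlier prosthesis. It reports: "These give sample size estimates of 4, and 9 subjects, respectively". It calls this conservative on two grounds: the test is two-tailed although directional changes are expected, and "it does not account for repeated-measures structure in our experimental design". From these it concludes "Therefore we expect 6-10 subjects to provide sufficient statistical power".

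The size is fixed at both ends of the section: "For specific tests with a goal of publication, the sample size will be 10 participants" and "We plan to use 10 subjects for the tests of prostheses and orthoses at UW Madison". The symbol d is defined as "the expected difference in outcome value, post- vs. pre-training".

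Under Specific Procedures, Intended Outcome - Primary reads: "The primary outcome is the measured difference in stride length at identical walking speed when using different prostheses, orthoses, or footwear". Study Outcomes in Part I sets a broader primary outcome, biomechanical gait function, which covers both kinematics and kinetics. Data Processing/Data Analysis plans repeated measures ANOVA with False Discovery Rate adjustment.

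**The concern.** Three things look wrong on a first reading.

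- The range starts at 6, although the formula has just asked for 9 for collision work. A reader might think 6 participants meet the 80% goal when the plan's own arithmetic says they do not.
- Of the two grounds for calling the estimate conservative, one-tailed testing sits poorly with an ANOVA F test, which has no direction. The gain from repeated measures is claimed without a correlation to size it.
- Both inputs are kinetic. The real-world comparison is about stride length at matched speed, and no expected difference or SD for it appears anywhere. The definition of d as a change over training also does not fit a comparison of devices.

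If the operative size rested on the low end of the range, the study could be too small for one of its two powered outcomes, and the power for stride length would be unknown.

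**Working it through.** **Inputs (Sample size section).** z = 1.96 and 0.84. Push-off: d/σ = 3.1/1.5 = 2.07. Collision work: d/σ = 0.055/0.04 = 1.375. The section does not say whether 0.04 is a per-condition SD or the SD of within-person differences, so both readings are shown.

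**Step 1: the plan's figures.** N = 2 × ((1.96 + 0.84) × σ/d)².
- Push-off: 2 × (2.80 × 1.5/3.1)² = 3.67, so 4.
- Collision work: 2 × (2.80 × 0.04/0.055)² = 8.29, so 9.

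Both match.

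**Step 2: power by the same formula,** Φ(d/σ × √(n/2) − 1.96).

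| n | Collision work | Push-off |
|---|---|---|
| 6 | 66.3% | 94.7% |
| 8 | 78.5% | 98.5% |
| 9 | 83.1% | 99.2% |
| 10 | 86.7% | 99.6% |

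The planned 10 passes 80% for both outcomes. Six passes for push-off only.

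**Step 3: collision work at n = 6, on the plan's two grounds.**
- One-tailed alone, by formula: 2 × ((1.645 + 0.84) × 0.04/0.055)² = 6.53, so 7 are needed; power at 6 is 76.9%.
- Repeated measures alone, with 0.04 as the SD of differences, two-sided paired t: 76.7% at 6 and 85.6% at 7. The normal approximation that the plan uses would give Φ(1.375 × √6 − 1.96) = 92%.
- Both together, one-tailed paired t: 89.0%.
- With 0.04 as a per-condition SD, the SD of differences is 0.04 × √(2(1 − ρ)). Power of 80% at n = 6 then needs ρ of about 0.33 one-tailed, or 0.54 two-sided.
- Three-device repeated measures ANOVA (sphericity, SD of differences 0.04, range of means 0.055): 73% with equally spaced means, 85% with two equal means.

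So 6 falls short on either ground alone, except under the normal approximation for paired data. It passes on both together if 0.04 is the SD of differences, or if it is per-condition and the correlation is moderate.

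**Step 4: n = 10 under the paired analysis, collision work.** With 0.04 as the SD of differences, two-sided paired t gives 97.1%. With 0.04 as a per-condition SD and zero correlation it gives 78.1%, and a correlation of about 0.05 restores 80%. A three-device ANOVA with 10 has 80% power for 0.93 to 1.07 SD of differences, which is below the 1.375 assumed.

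**Step 5: stride length.** With no difference or SD given, only a standardised figure is possible. Ten completers detect 0.996 SD of within-person differences at 80% power (two-sided paired t); 8 completers detect 1.156 SD. By the plan's formula, 10 detect 2.80 × √(2/10) = 1.25 per-condition SD. These are properties of n = 10 for any outcome and say nothing specific about stride length.

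**The case for a change.** The strongest case for a change is the stride-length gap. It is the named primary outcome of the real-world comparison, it has no power input, and laboratory kinetics do not describe participants set up off site, who have no lab testing. The drop-foot target is also exactly 10, with no allowance for dropout, and False Discovery Rate adjustment is left out of the calculation. Rewording would cost nothing.

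Much of this is factually right. No stride-length input exists. The training wording is a slip. The one-tailed ground does not fit an F test, although the protocol does predict longer strides with more compliant feet or with electrical stimulation. The margin at 10 is also limited: by the plan's formula, collision work has 83.1% with 9 completers and 78.5% with 8. A Bonferroni-type alpha of 0.05/3 for three device pairs would give 75.2% at 10, and False Discovery Rate control is less strict than that.

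None of it changes what the study does. A sentence in SD units would add no knowledge about stride length. If it were set beside the kinetic figures it would rest on a different SD scale (1.0 SD of differences against 1.25 per-condition SD), which invites misreading. The two primary-outcome statements differ in scope: the one in Part I covers the whole project and includes the powered kinetic measures, while the other belongs to the real-world procedures. Ten is the size of a specific test, whereas Target Population and Enrollment plans 20 participants with transtibial amputation, so the 8-completer case does not carry over to the prosthesis group.

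**Conclusion.** The concern does not call for a change. The estimates of 4 and 9 are correct, and the operative size of 10 meets the 80% goal for both powered outcomes: 99.6% for push-off and 86.7% for collision work, by the plan's formula for one unadjusted comparison with all 10 completing. The lower end of the range is a loose remark. For collision work at 6, power is 66% by formula, 77% on either of the plan's grounds alone (one-tailed formula, or two-sided paired t), and 89% on both together if 0.04 J/kg is the SD of differences. That leaves 6 unquantified rather than refuted, and no decision rests on it.

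The missing stride-length input is a gap that the documents' own data cannot fill. An analyst would report the stride-length difference with its interval and judge precision from that. The training phrase is clerical: the rest of the protocol makes plain that d is a difference between devices. This conclusion assumes that specific tests are run with 10 participants, as the section states. If a test were run with 6, the unstated correlation would matter.
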